9.4. Appendix D Imputation Rules for Missing AE dates

Imputation rules for missing or partial AE start dates and stop dates are defined below:

3. Missing or partial AE start date:

- If only DAY is missing, use the first day of the month, unless:
 - The AE end date is after the date of first injection or is missing AND the start month and year of the AE coincide with the start month and year of the first injection. In this case, use the date and time of first injection, even if time is collected.
- If DAY and Month are both missing, use the first day of the year, unless:

- The AE end date is after the date of first injection or is missing AND the start year of the AE coincides with the start year of the first injection. In this case, use the date of first injection
 - If DAY, Month and Year are all missing, the date will not be imputed. However, if the AE end date is prior to the date of first injection, then the AE will be considered a pre-treatment AE. Otherwise, the AE will be considered treatment-emergent.
4. Missing or partial AE end dates will not be imputed.

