3.4. Primary Endpoints (Part B, Open Label)

3.4.1. Primary Safety Endpoints

The primary safety objective will be evaluated by the following safety endpoints:

- Solicited local and systemic ARs through 7 days after each injection.
- Unsolicited AEs through 28 days after each injection.
- MAAEs through the entire study period.
- SAEs throughout the entire study period.
- Vital sign measurements and physical examination findings.

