For calculation regarding antibody levels/titers:

Part A:

Antibody values reported as below the LLOQ will be replaced by $0.5 \times \text{LLOQ}$. Values that are greater than the upper limit of quantification (ULOQ) will be converted to the ULOQ. Missing results will not be imputed.

Part B:

Antibody values reported as below the LLOQ will be replaced by $0.5 \times \text{LLOQ}$. Values that are greater than the ULOQ and without actual values reported (eg, '>xxx') will be converted to the ULOQ. Values that are greater than the ULOQ and with actual values reported will not be imputed. Missing results will not be imputed.

This study can be divided into the following **stages**:

- Vaccination stage:

Part A:

For assessments that will be collected throughout the study (eg, unsolicited AE), it consists first injection on Day 1 to 28 days after last injection in Part A (ie, the day of last injection and 27 subsequent days).

For assessments that will be collected at study visits (eg. laboratory and vital sign), if a subject receives two injections, this stage starts at the first injection on Day 1 and continues through Month 2 visit; If a subject receives first injection only, this stage starts at the first injection on Day 1 and continues through Month 1 visit.

Part B:

For assessments that will be collected throughout the study (eg, unsolicited AE), it consists first injection on OL-Day 1 to 28 days after last injection in Part B (ie, the day of last injection and 27 subsequent days).

For assessments that will be collected at study visits (eg. laboratory and vital sign), if a subject receives two injections, this stage starts at the first injection on OL-Day 1 and continues through OL-M2 visit; If a subject receives first injection only, this stage starts at the first injection on OL-Day 1 and continues through OL-M1 visit.

- Follow up stage:

Subjects who did not receive dose in Part B:

Consists of all periods that begin 28 days after the last injection in Part A (ie, the day of last injection in Part A + 28 days, regardless of number of injections received) and continue until the earliest date of (study completion, discontinuation from the study, or death).

Subjects who received dose in Part B:

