Consists of all periods that begin 28 days after the last injection in Part A (ie, the day of last injection in Part A + 28 days, regardless of number of injections received) and continue until the earliest date of first injection in Part B, and all periods that begin 28 days after the last injection in Part B (ie, the day of last injection in Part B + 28 days, regardless of number of injections received) and continue until the earliest date of (study completion, discontinuation from the study, or death).

- Day 1 to End of Study: Begins at the first injection on Day 1 and continues through the earliest date of (study completion, discontinuation from the study, or death).
- 28 days after any vaccination stage: This stage starts at the day of each vaccination and continue through the earliest date of (the day of each vaccination and 27 subsequent days, next vaccination (if applicable)).

Unscheduled visits: Unscheduled visit measurements will be included in analysis as follows:

- In scheduled visit windows per specified visit windowing rules.
- In the derivation of baseline/last on-treatment measurements.
- In the derivation of maximum/minimum on-treatment values and maximum/minimum change from baseline values for safety analyses.
- In individual subject data listings as appropriate.

Visit windowing rules: The analysis visit windows for protocol-defined visits are provided in [Appendix B](#).

Incomplete/missing data:

- Imputation rules for missing prior/concomitant medications, non-study vaccinations and procedures are provided in [Appendix C](#).
- Imputation rules for missing AE dates are provided in [Appendix D](#).
- For laboratory assessments, if majority of results are indefinite, imputation of these values will be considered. If the laboratory results are reported as below the LLOQ (eg, <0.1), the numeric values will be imputed by $0.5 \times \text{LLOQ}$ in the summary. If the laboratory results are reported as greater than the ULOQ (eg, >3000), the numeric values will be imputed by ULOQ in the summary.

- Other incomplete/missing data will not be imputed, unless specified otherwise.

The following vaccination **groups** will be used for summary purposes:

- Part A, Blinded Phase:
 - mRNA-1273 50 µg
 - mRNA-1273 100 µg
 - mRNA-1273 Total
 - Placebo
- Part B, Open-Label Phase:
 - mRNA-1273 50 µg - Booster
 - mRNA-1273 100 µg - Booster
 - mRNA-1273 - Booster Total
 - Placebo - mRNA-1273

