6.3.1. Adverse Events

A treatment-emergent AE (TEAE) is defined as any event not present before exposure to study vaccine or any event already present that worsens after exposure to study vaccine. [Note: worsening of a pre-existing condition after vaccination will be reported as a new AE.]

Adverse events will also be evaluated by the investigator for the coexistence of MAAE which is defined as an AE that leads to an unscheduled visit to a healthcare practitioner.

Unsolicited AEs will be coded by PT and SOC using MedDRA and summarized by age cohort, vaccination group, and stage (28 days after any vaccination stage for Part A and Part B separately, and Day1 to End of Study; see [Section 6.1](#) for definitions of vaccination group and stage).

All summary tables (except for the overall summary of AEs) for unsolicited AEs will be presented by SOC and PT for TEAEs with counts of subjects included. SOC will be displayed in internationally agreed order. PT will be displayed in descending order of frequency of total mRNA-1273 and then alphabetically within SOC. When summarizing the number and percentage of subjects with an event, subjects with multiple occurrences of the same AE or a continuing AE will be counted once. Subjects will be presented

according to the highest severity (the strongest relationship) in the summaries by severity (of related AEs), if subjects reported multiple events under the same SOC and/or PT.

Percentages will be based upon the number of subjects in the Safety Set within each vaccination group.

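### Appendix D of the Part A/B SAP ties partial adverse event dates to an unqualified first injection; read literally, it can date a post-booster event before the booster and out of the Part B 28-day summary

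*SAP*

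**What the plan says.** Appendix D of the Part A/B SAP sets two defaults for partial AE start dates. For a missing day: "If only DAY is missing, use the first day of the month, unless" an exception applies. For a missing day and month: "If DAY and Month are both missing, use the first day of the year, unless" the same kind of exception applies, by year. The exception uses the date of first injection if the end date is later or missing and the "start month and year of the AE coincide with the start month and year of the first injection". No Part is named, and later injections have no rule.

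A Part B primary safety endpoint (SAP 3.4.1) is "Unsolicited AEs through 28 days after each injection". SAP 6.3.1 summarises unsolicited AEs by stage: "28 days after any vaccination stage for Part A and Part B separately, and Day1 to End of Study". SAP 6.1 defines the first of these: "28 days after any vaccination stage: This stage starts at the day of each vaccination". It runs for 27 further days or until the next vaccination. A date more than 28 days after the last Part A dose but before the first Part B dose belongs to the follow-up stage.

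**The concern.** The exception stops a partial date from moving an event to before a dose it may have followed. It does this for one injection only. SAP 6.1 distinguishes the first injection in Part A from the first injection in Part B when it defines study day, and it uses the unqualified first dose as the general baseline before giving separate Part B baselines. Table 5 in Appendix C qualifies the last injection by Part but not the first. On that evidence the literal meaning in Appendix D is Part A Day 1.

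If so, the default moves uncertain Part B events backwards, which is the less cautious direction for a safety summary. It is also the less likely direction. Protocol 3.4.8.7 ends routine unsolicited AE capture in Part A at the Day 57 visit, so an ordinary unsolicited AE recorded in the booster month most likely began after the booster. SAP section 1 states that Part A is complete and reported, so Part B is where this appendix still has work to do.

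**Working it through.** The plan gives no figure on this point, so there is none to reproduce. The check applies the written rule to dates.

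**Inputs from the documents**
- All 3 × 200 = 600 first doses in Part A had been given by 5 Nov 2020 (Protocol 1.3).
- Part B was introduced by Amendment 4, dated 15 Jan 2021 (Protocol 7.3.2).
- The 28-day stage is the vaccination day plus 27 days (SAP 6.1).

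**Assumptions, not in the documents**
- Booster dates are uniform from 16 Jan to 31 Dec 2021 (350 days).
- True onset is uniform over the booster day and the next 27 days.
- The end date is missing or not before the booster.

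**Step 1: can the exception apply?** Part A first doses fall in 2020 and Part B doses in 2021 or later. They share neither month nor year, so on the literal reading the exception never applies to a Part B dose.

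**Step 2: one case.** Booster 15 Mar 2021, onset 20 Mar 2021, day missing. The imputed date is 1 Mar 2021, 14 days before the booster and outside the stage. Anchored to the Part B dose, it would be 15 Mar 2021, inside the stage.

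**Step 3: share affected when only the day is missing.** For a booster on day d of a month with L days, the onset days that lie in the same month and in the window number min(28, L − d + 1). All are lost if d ≥ 2. An onset in the next month is dated to the 1st of that month, which lies between booster and onset, so it stays in. Summing over d = 2 to L, with 27 + 26 + … + 1 = 378:
- 31-day month: 3 × 28 + 378 = 462
- 30-day month: 2 × 28 + 378 = 434
- February: 378
- 16–31 January: 16 + 15 + … + 1 = 136

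Total lost: 136 + 378 + 6 × 462 + 4 × 434 = 5,022. All combinations: 350 × 28 = 9,800. Share: 5,022 / 9,800 = 51.2%.

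Boosters on the 1st of a month (11 × 28 = 308 combinations) are unaffected. Among onsets in the booster month itself the share is 5,022 / (5,022 + 308) = 5,022 / 5,330 = 94.2%.

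**Step 4: day and month missing.** An onset in 2021 becomes 1 Jan 2021, before any Part B dose. Every such event drops out of the Part B stage.

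**Step 5: would naming the Part be enough?** With OL-Day 1 as anchor, 0 of 9,800 single-booster combinations are lost. For former placebo recipients given two doses, an OL-Day 1 anchor alone still loses second-dose events once the gap exceeds 28 days, because the 1st of the month can fall after the first dose's stage has ended and before the second dose. The loss is 0% at 28 days, about 9% at 31 days and about 22% at 35 days (28 plus the +7 allowance in Protocol Table 11).

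**The case against.** The strongest reply is that the Part A reading is an inference. The SAP sometimes drops the Part label while meaning Part B. The Part B vaccination stage in 6.1 speaks of a subject who receives the first injection only, and the OL-Day 29 immunogenicity row of Table 4 says second injection without a Part, although the vital-sign row names it. SAP 6.3 also requires safety analyses separately by Part. A programmer could reasonably read Appendix D per Part, and would then lose no single-booster event. This stands as a limit on certainty. It does not clear the text, because two defensible readings give different Part B counts and the per-Part reading still misses some second-dose events.

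The consequence is also bounded. A misdated event remains treatment-emergent and stays in the Day 1 to End of Study summary and the listings. The medically attended and serious AE endpoints cover the whole study. Solicited reactions are recorded daily in the eDiary. Protocol 3.4.8.8 collects time of onset for unsolicited AEs, and visits are frequent in the first month, so missing days should be uncommon.

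A reader might infer that Appendix C has the same fault for medications. The documents do not support that in effect. SAP 6.2.4 counts medications that continued past the first injection in either Part, so a drug dated too early but still in use after the booster is counted.

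**Conclusion.** The point holds as a small defect in Appendix D for Part B. On the literal reading, about 51% of day-missing events in the 28 days after the booster, and all year-only events in the booster year, fall outside a primary safety summary. The 51% rests on uniform booster and onset dates and is conditional on the day being missing.

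A reader might infer that booster AEs as a whole are undercounted by about half, or that events vanish from the report. Neither follows. The documents give no count of partial dates, that count is probably small, and affected events are misplaced within the summaries, not deleted.

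**What to change.** Add to Appendix D, for Part B analyses only:

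- If the AE start month and year (or the year alone, when the month is also missing) match those of a Part B injection, and the AE end date is on or after that injection or missing, impute the date of that injection.
- If both Part B injections match, use the most recent one not later than the AE end date.

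Leave Part A imputation as it is, since its reports are final, and leave Appendix C alone. With this rule no event that truly began in the 28 days after a Part B dose is lost. It is either dated to a matching dose or dated to the start of a later month or year, which lies between the dose and the true onset.

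The cost is one SAP sentence and a small program change; no new data are needed. The downside is that a few pre-booster events may be counted as post-booster and, when only the year is known, some late follow-up events may be drawn into the 28-day window. Both err in the conservative direction for a safety summary.

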This statistical analysis plan (SAP), which describes the planned analyses for Part C of Study mRNA-1273-P201, is based on the most recent approved clinical study protocol (CSP), Version Amendment 6, dated 28-APR-2021. The most recent approved electronic case report form (eCRF) Version 5.005, dated 24-FEB-2021.

In addition to the information presented in the statistical analysis plan section of the protocol (Section 4) which provides the principal features of analyses for this study, this SAP provides statistical analysis details/data derivations. It also documents modifications or additions to the analysis plan that are not “principal” in nature and result from information that was not available at the time of protocol finalization.

Study mRNA-1273-P201 is a Phase 2a, randomized, observer-blind, placebo-controlled, dose-confirmation study to evaluate the safety, reactogenicity, and immunogenicity of messenger ribonucleic acid (mRNA)-1273 SARS-CoV-2 vaccine in adults who aged 18 years and older. Part C is added in the CSP Amendment 5 to investigate the proof of concept of a single dose booster of two dose levels of the mRNA-1273.351 variant and a mixture formulation of mRNA-1273/mRNA-1273.351 administered to approximately 60 participants who received primary vaccination during the mRNA-1273-P301 COVE study.

PPD Biostatistics and programming team, designee of Moderna Biostatistics and Programming department, will perform the statistical analysis of the safety, reactogenicity, and immunogenicity data; Statistical Analysis System (SAS) Version 9.4 or higher will be used to generate all statistical outputs (tables, figures, listings, and datasets). The SAP will be finalized and approved prior to the interim (primary) analysis for Part C of the study. If the methods in this SAP differ from the methods described in the protocol, the SAP will prevail.

2. Study Objectives

2.1. Primary Objective

2.1.1. Primary Safety Objective

The primary safety objective is to evaluate the safety and reactogenicity of 2 dose levels (20 and 50 µg) of mRNA-1273.351 or one dose level of mRNA-1273/mRNA-1273.351 mixture (50 µg total) vaccine administered as a single booster dose after completing a two-dose vaccination schedule of mRNA-1273 at least 6 months earlier.

2.1.2. Primary Immunogenicity Objective

[figure not shown]
The primary immunogenicity objective is to evaluate the immunogenicity of 2 dose levels (20 and 50 µg) of mRNA-1273.351 or one dose level of mRNA-1273/mRNA-1273.351 mixture (50 µg total) vaccine administered as a single booster dose after completing a two-dose vaccination schedule of mRNA-1273 at least 6 months earlier, as assessed by the level of specific neutralizing antibody (nAb) directed against the S2P antigen derived from B.1.351 variant.

2.2. Secondary Immunogenicity Objectives

The secondary immunogenicity objective is to evaluate the immunogenicity of 2 dose levels (20 and 50 µg) of mRNA-1273.351 or one dose level of mRNA-1273/mRNA-1273.351 mixture (50 µg total) vaccine administered as a single booster dose after completing a two-dose vaccination schedule of mRNA-1273 at least 6 months earlier, as assessed by the level of specific binding antibody (bAb) directed against the S2P antigen derived from B.1.351 variant.

2.3. Exploratory Objectives

The exploratory objectives are the following:

3. Study Endpoints

3.1. Primary Endpoints

3.1.1. Primary Safety Endpoints

The primary safety objective will be evaluated by the following safety endpoints:

- Solicited local and systemic adverse reactions (ARs) through 7 days after injection.
- Unsolicited adverse events (AEs) through 28 days after injection.
- Medically-attended AEs (MAAEs) through the entire study period.
- Serious AEs (SAEs) throughout the entire study period.
- Vital sign measurements and physical examination findings.

3.1.2. Primary Immunogenicity Endpoints

The primary objective will be evaluated by the following endpoints:

- For participants receiving 2 dose levels (20 and 50 μ g) of mRNA-1273.351 or one dose level (50 μ g total) of mRNA-1273/mRNA-1273.351 mixture as a single booster: titer of serum nAb against SARS-CoV2 as measured by pseudovirus (and/or live virus) using the B.1.351 and D614G variant sequences of SARS-CoV-2 protein (and/or variant strains) on OL-Day 1, OL-Day 8, OL-Day 15, and OL-Day 29 (OL-Month 1), OL-Day 57 (OL-Month 2), and OL-Day 181 (OL-Month 6).
- For participants receiving 2 dose levels (20 and 50 μ g) of mRNA-1273.351 or one dose level (50 μ g total) of mRNA-1273/mRNA-1273.351 mixture as a single booster: seroconversion on OL-Day 8, OL-Day 15, and OL-Day 29 (OL-Month 1), OL-Day 57 (OL Month 2), and OL-Day 181 (OL-Month 6) and the proportion of participants with a ≥ 2 -, ≥ 3 -, or ≥ 4 -fold rise in antibody titer from open-label baseline.

[figure not shown]
3.2. Secondary Immunogenicity Endpoints

For participants receiving 2 dose levels (20 and 50 μ g) of mRNA-1273.351 or one dose level (50 μ g total) of mRNA-1273/mRNA-1273.351 mixture as a single booster: level of SARS-CoV-2-specific bAb against the B.1.351 and D614G variant sequences of

SARS-CoV-2 protein on OL-Day 1, OL-Day 8, OL-Day 15, OL-Day 29 (OL-Month 1), OL-Day 57 (OL-Month 2), and OL-Day 181 (OL-Month 6).

3.3. Exploratory Endpoints

The exploratory endpoints are the following:

4. Study Design

[figure not shown]
4.1. Overall Study Design

This is a three-part, Phase 2a study: Part A, Part B, and Part C. Please refer to the study Protocol for details regarding Part A and Part B. Part C will be a Proof-of-Concept rollover study of approximately 60 participants, who are currently enrolled in Moderna's Phase 3 mRNA-1273-P301 COVE study, and have previously received 2 doses of mRNA-1273 at least 6 months earlier. At enrollment of this study, their participation in mRNA-1273-P301 COVE study will be terminated. The study schematic for Part C is presented in [Figure 1](#).

Part C, the Open-Label Interventional Phase of the study of mRNA-1273.351 and mRNA-1273/mRNA-1273.351 mixture booster vaccines, is prompted by the need to pro-actively prepare for vaccination strategies that induce a broader protection, including variants such as B.1.351. Upon consent to roll over, Participants in Part C will receive a single booster dose of either mRNA-1273.351 (20 μ g or 50 μ g), or mRNA-1273/mRNA-1273.351 mixture (50 μ g total). An additional booster dose may be added approximately 56 days after the first boost at OL-D1. This additional booster dose will be triggered following review of immunogenicity data up to OL-Day 15 of the initial mRNA-1273.351 (20 μ g and 50 μ g) and mRNA-1273/mRNA-1273.351 mixture injections. The enrollment and

vaccination in each study arm will be sequential. The first 20 participants will be enrolled and dosed on OL-Day 1 with mRNA-1273.351 50 μ g dose. Upon completion of the first 50 μ g dose arm, 20 participants will be enrolled in the second arm and will receive the mRNA-1273/mRNA-1273.351 mixture (50 μ g total dose). Following completion of the second arm, 20 participants will be enrolled and dosed with in the mRNA-1273.351 20 μ g dose.

Figure 1 Study Design Schematic

4.2. Sample Size and Power

There is no hypothesis testing in this study. The number of proposed participants is considered sufficient to provide a preliminary summary of the safety and immunogenicity.

In the open-label Part C, approximately 60 participants from Moderna's mRNA-1273-P301 COVE study, will be enrolled and will be assigned to receive a single intramuscular injection of mRNA-1273.351 (20 μ g or 50 μ g) or mRNA-1273/mRNA-1273.351 mixture (50 μ g total). The enrollment and vaccination in each study arm will be sequential. The first 20 participants will be enrolled and dosed on OL-Day 1 with mRNA-1273.351 50 μ g dose. Upon completion of the first 50 μ g dose arm, 20 participants will be enrolled in the second arm and will receive the mRNA-1273/mRNA-1273.351 mixture (50 μ g total dose).

Following completion of the second arm, 20 participants will be enrolled and dosed with the mRNA-1273.351 20 µg dose.

4.3. Randomization

Part C will be open label and Interactive Response Technology (IRT) system will not be utilized. The enrollment and vaccination in each study arm will be sequential. The first 20 participants will be enrolled and dosed on OL-Day 1 with mRNA-1273.351 50 µg dose. Upon completion of the first 50 µg dose arm, 20 participants will be enrolled in the second arm and will receive the mRNA-1273/mRNA-1273.351 mixture (50 µg total dose). Following completion of the second arm, 20 participants will be enrolled and dosed with the mRNA-1273.351 20 µg dose.

